9.7.1.6.1 PRIMARY EFFICACY ANALYSIS

Primary analysis of primary endpoint

The primary analysis will be based on MCI/Prodromal subjects from the FAS with the prespecified censoring rule applied. The primary endpoint is the change from baseline to 18 months in the derived ADCOMS. The dose-response of the primary endpoint is modelled with a first-order normal dynamic linear model, where Normal and Inverse-Gamma priors are used. The primary efficacy analysis will calculate the Bayesian posterior probability that the dose identified is the most likely ED₉₀ dose that achieves 25% improvement over the placebo arm. At each interim analysis and the final analysis, 2 Bayesian probabilities will be summarized for each active dose: the probability it is the ED₉₀ dose and the probability of achieving 25% improvement over the placebo arm.

For the clinical efficacy data (ie, derived ADCOMS, MMSE, CDR, ADAS-cog, CBB, ISLT, and FAQ) subjects will be censored at the time of initiation of treatment with AChEIs or memantine, if they were not on these medications at the time of Baseline cognitive assessment (Visit 2), and will be censored at the time of dose adjustment of AChEIs or memantine if they were already on stable treatment with these medications at the time of Baseline cognitive assessment (Visit 2). The value of the primary endpoint for censored subjects will be imputed using data up to the censoring time and Bayesian longitudinal modeling.

Sensitivity analysis of primary endpoint

After unblinding, the primary endpoint will be analyzed using the Bayesian methods described above as well as conventional statistical methods. The following additional Bayesian analyses will be conducted as sensitivity analyses:

- The primary endpoint will be analyzed regardless of initiation of treatment, or dose adjustment, with AChEIs or memantine using the same Bayesian analysis method as primary analysis. This is an intent-to-treat analysis without any censoring.
- In case of early success, the primary analysis as well as the above sensitivity analyses will be repeated after all subjects have completed 18 months of treatment or have been lost to follow-up.

Statistical methods for the final conventional analyses will use a mixed-effects model with repeated measures (MMRM) on the change from baseline in the derived ADCOMS at 18 months. The model will include treatment groups, randomization stratification variables (the presence or absence of ongoing treatment with AChEIs or memantine or both, and *ApoE4* status), and baseline ADCOMS as covariates. Other covariates such as adjusted hippocampal volume will be studied. These analyses will be performed as sensitivity analyses on the FAS as well as the PP set and as such, no multiplicity adjustments will be made to account for the interim analyses. In case of early success, the conventional analyses will also be performed using the data collected before the interim analysis.

9.7.1.6.2 SECONDARY EFFICACY ANALYSES

The MCI/Prodromal Cohort

An MMRM will be used to analyze the following secondary endpoint: (revised per Amendment 02)

- Change from baseline in total hippocampal atrophy at 12 and 18 months of treatment in MCI/Prodromal subjects as measured by vMRI

Comparisons between each treatment group and placebo will be performed.

The Mild to Moderate AD Cohort (revised per Amendment 01)

The MMRM will be used to analyze the change from baseline of derived ADCOMS at 18 months in mild to moderate AD. If there is no treatment group-by-population interaction in the overall study, the MMRM analysis will include all subjects (MCI/Prodromal or mild to moderate AD) in the overall study. Otherwise, the MMRM analysis will only include subjects in the Mild to Moderate AD cohort. The comparison between placebo and active doses will be performed within mild to moderate AD subjects regardless of subjects included in the MMRM analysis. Dunnett's method will be used to control for multiplicity due to multiple comparisons.

9.7.1.6.3 EXPLORATORY EFFICACY ANALYSES

(revised per Amendments 01 and 02)

An MMRM will be used to analyze the following exploratory endpoints:

- Change from baseline in the derived ADCOMS at 12 months in MCI/Prodromal and mild to moderate AD subjects
- Change from baseline in total hippocampal atrophy at 12 and 18 months in mild to moderate AD subjects as measured by vMRI
- Change from baseline in CSF A β (1-x) and CSF A β (1-42) after 4 weeks and 18 months in MCI/Prodromal and mild to moderate AD subjects. Data from early discontinuations will also be included.
- Change from baseline in the clinical assessments: ADAS-cog, CDR, MMSE, ISLT, CBB, and FAQ at 12 weeks and at 6, 9, 12, 15, 18, 19, and 21 months in MCI/Prodromal and mild to moderate AD subjects
- Change from baseline in plasma and CSF amyloid and CSF BACE1 measurements after 4 weeks and 18 months of treatment, and during posttreatment follow-up in MCI/Prodromal and mild to moderate AD subjects
- Change from baseline in left and right hippocampal, whole brain, and total ventricular volume at 6, 12 and 18 months as measured by vMRI in MCI/Prodromal and mild to moderate AD subjects

A linear mixed-model will be used to analyze the following exploratory endpoints:

- Change from baseline in brain amyloid levels as measured by amyloid PET at 18 months in MCI/Prodromal and mild to moderate AD subjects
- Change from baseline in CSF biomarkers of neurodegeneration (eg, tau, p-tau) at 18 months of treatment in MCI/Prodromal and mild to moderate AD subjects

Data from early discontinuations will also be used as appropriate. Comparisons between each treatment group and placebo will be performed.

A linear mixed-model with repeated measures will be used to determine the relationship between the following endpoints:

- Change from baseline in the derived ADCOMS score and the change from baseline in biomarkers in CSF at 18 months in MCI/Prodromal and mild to moderate AD subjects
- Change from baseline in the derived ADCOMS score and change from baseline in imaging biomarkers (hippocampal, whole brain, and total ventricular volumes) at 12 and 18 months in MCI/Prodromal and mild to moderate AD subjects

ApoE status for heterozygous and homozygous E4 carriers will be included in the model to assess the effect of *ApoE* status in this relationship.

9.7.1.7 Pharmacokinetic, Pharmacodynamic, Pharmacogenomic, and Other Biomarker Analyses

9.7.1.7.1 PHARMACOKINETIC ANALYSES

The Safety Analysis Set will be used for individual E2609 concentration listings. The PK Analysis Set will be used for summaries of E2609 concentrations.

9.7.1.7.2 PHARMACODYNAMIC, PHARMACOGENOMIC, AND OTHER BIOMARKER ANALYSES

Pharmacodynamic, PGx, and other biomarker analyses may be performed and reported separately. Details of these analyses may be described in a separate statistical analysis plan. Please also refer to [Appendix 3](#).

Pharmacodynamic Analyses

The PD Analysis Set will be used for the summaries and analyses of PD biomarkers (CSF and plasma biomarkers, MRI endpoints). CSF A β (1-x), A β (1-42), t-tau, p-tau, and BACE1 will be assessed and data will be presented graphically. Baseline levels and changes in t-tau and p-tau will be correlated with changes in CSF A β (1-42), imaging markers, and *ApoE4* status.

Summary statistics for CSF biomarkers will be assessed for evidence of a dose relationship.

Pharmacokinetic and Pharmacodynamic Analyses

The PK/PD relationship between CSF biomarker levels and exposure to E2609 in CSF will be explored graphically and any emergent relationship will be explored through population PK/PD modeling. The PK/PD relationship between plasma PK parameters with other biomarkers may also be explored using similar methods.

Additionally, the relationship between plasma and CSF exposure to E2609 and the derived ADCOMS at 18 months, and the relationship between plasma and CSF exposure to E2609 and the change from baseline for 18 months in the ADAS-cog, the CDR, and the MMSE, will be explored graphically. Any emergent relationship will be explored through population PK/PD modeling.

Exposure-safety analyses may also be conducted.

Pharmacogenomic Analyses

Blood samples will be used to determine the *ApoE* genotype and the *NAT2* phenotype of subjects enrolled in this study. The genomic DNA samples may also be stored and used as

described in [Section 9.7.1.7.2](#). Details of PGx testing may be provided and reported separately.

9.7.1.8 Safety Analyses

Evaluations of safety will be performed on the Safety Analysis Set. The incidence of AEs (including changes from baseline in physical and neurological examinations, and dermatological assessments), out-of-normal-range laboratory safety test variables, abnormal ECG findings, out-of-range vital signs, suicidality (C-SSRS), and results of the sleep questionnaire, along with the change from baseline in laboratory safety test variables, ECGs, safety MRI, and vital sign measurements will be summarized by treatment group using descriptive statistics.

9.7.1.8.1 EXTENT OF EXPOSURE

The extent of exposure to study drug will be summarized as cumulative extent of exposure in 3-month intervals. The number and percent of subjects will be presented by treatment group. Duration of exposure will be summarized using descriptive statistics in 3-month intervals. The number and percent of subjects will be presented by treatment group.

9.7.1.8.2 ADVERSE EVENTS

The AE verbatim descriptions (investigator terms from the eCRF) will be classified into standardized medical terminology using the Medical Dictionary for Regulatory Activities (MedDRA). Adverse events will be coded to the MedDRA (Version 17.0 or higher) lower level term closest to the verbatim term. The linked MedDRA preferred term and primary system organ class (SOC) are also captured in the database.

A TEAE is defined as an AE that emerges during treatment, having been absent at pretreatment (Baseline) or

- Reemerges during treatment, having been present at pretreatment (Baseline) but stopped before treatment, or
- Worsens in severity during treatment relative to the pretreatment state, when the AE is continuous.

Only those AEs that are treatment-emergent will be included in summary tables. All AEs, treatment-emergent or otherwise, will be presented in subject data listings.

The TEAEs will be summarized by treatment group on the Safety Analysis Set. The incidence of TEAEs will be reported as the number (percentage) of subjects with TEAEs by SOC and preferred term. A subject will be counted only once within an SOC and preferred term, even if the subject experienced more than 1 TEAE within a specific SOC and preferred term. The number (percentage) of subjects with TEAEs will also be summarized by maximum severity (mild, moderate, or severe). The number (percentage) of subjects with

TEAEs will also be summarized by relationship to study drug (Yes [related] and No [not related]).

The number (percentage) of subjects with treatment-related TEAEs will be summarized by SOC and preferred term. Treatment-related TEAEs include those events considered by the investigator to be related to study drug. The number (percentage) of subjects with treatment-related TEAEs will also be summarized by maximum severity (mild, moderate, or severe).

Adverse events will be summarized by the following subgroups: *ApoE4* status (positive or negative), prior treatment with AChEIs or memantine (no or yes), and clinical population (MCI/Prodromal or mild to moderate AD). (revised per Amendment 01)

The number (percentage) of subjects with TEAEs leading to death will be summarized by MedDRA SOC and preferred term for each treatment group. A subject data listing of all AEs leading to death will be provided.

The number (percentage) of subjects with treatment-emergent SAEs will be summarized by MedDRA SOC and preferred term for each treatment group. A subject data listing of all SAEs will be provided.

The number (percentage) of subjects with TEAEs leading to discontinuation from study drug will be summarized by MedDRA SOC and preferred term for each treatment group. A subject data listing of all AEs leading to discontinuation from study drug will be provided.

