Stage B will be conducted globally and will enroll, randomize, and dose additional eligible subjects up to a maximum of 500 MCI/Prodromal subjects and up to a maximum of 200 mild to moderate AD subjects. The final total number of MCI/Prodromal subjects will depend upon whether the prespecified criteria for either early success or futility are met. (revised per Amendment 01)

In Stage B, both cohorts will include separate placebo groups. The MCI/Prodromal cohort will include 3 doses of E2609 (5, 15, and 50 mg QD), whereas the Mild to Moderate AD cohort will only include 2 doses of E2609 (15 and 50 mg QD). (revised per Amendment 01)

Bayesian response adaptive randomization will be used in the MCI/Prodromal cohort during Stage B. Randomization of MCI/Prodromal subjects into Stage B will commence according to a fixed schedule (1:1:1:1; placebo:5 mg E2609:15 mg E2609:50 mg E2609) until a total of 100 MCI/Prodromal subjects (including those from Stage A) have been randomized. (revised per Amendment 01) The remaining subjects in the MCI/Prodromal cohort in Stage B will then be randomized according to response adaptive randomizations based on the ADCOMS results using the Bayesian interim efficacy analyses. The mild to moderate AD subjects will be randomized according to a fixed schedule (1:1:1 placebo; 15 mg E2609; 50 mg E2609) throughout Stage B. (revised per Amendment 01)

Interim efficacy analyses are planned and are discussed in [Section 9.7.3](#).

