9.7.1.2 Definitions of Analysis Sets

- The Randomized Set is the group of subjects who are randomized to study drug.
- The Safety Analysis Set is the group of subjects who receive at least 1 dose of study drug and have at least 1 postdose safety assessment.
- The Full Analysis Set (FAS) is the group of randomized subjects who receive at least 1 dose of study drug and have baseline and at least 1 postdose primary efficacy measurement.
- The Per Protocol (PP) Analysis Set is the subset of subjects in the FAS who sufficiently comply with the protocol. The PP Analysis Set will be used to conduct a sensitivity analysis of the primary efficacy endpoint. Details of the evaluability criteria will be determined before database lock and treatment unblinding, and will be specified in the statistical analysis plan.

- The PK Analysis Set is the group of subjects with at least 1 quantifiable E2609 plasma concentration accompanied by a documented dosing history.
- The PD Analysis Set is the group of subjects who have a baseline PD measurement and at least 1 posttreatment PD measurement.

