9.7.4 Other Statistical/Analytical Issues

Adaptive Randomization in the MCI/Prodromal Cohort

Randomization to placebo or 1 of 3 dose groups of E2609 will be fixed for the first 100 MCI/Prodromal subjects randomized in the study (1:1:1:1; placebo to each of the 3 active doses for the first 100 MCI/Prodromal subjects randomized, including those randomized from both Stage A and Stage B). Thereafter, randomization probabilities to each treatment group will be updated at each interim analysis, such that the randomization probability will be increased for the placebo group and dosage groups that represent the potential target dose (ED_{90}), and simultaneously decreased for other active arms. (revised per Amendment 01)

Randomization in the Mild to Moderate AD Cohort (revised per Amendment 01)

In Stage A, the mild to moderate AD subjects will be randomized to placebo or 1 of 3 E2609 dose groups (5, 15, and 50 mg of E2609) at a 1:1:1:1 ratio, while in Stage B, the mild to moderate AD subjects will be randomized to placebo or 1 of 2 E2609 dose groups (15 and 50 mg E2609) at a 1:1:1 ratio. (revised per Amendment 01)

Stratification (revised per Amendment 01)

Within the 2 clinical cohorts (MCI/Prodromal and mild to moderate AD), subjects will be stratified at randomization by *ApoE4* status (positive or negative) and prior treatment with AChEIs or memantine or both (yes or no). (revised per Amendment 01)

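### Safety summaries by treatment group pool two cohorts with different arms and allocation ratios, and the protocol's split by clinical population is stated only for adverse events

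*Protocol*

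**What the plan says.** Section 9.7.1.2 defines one safety population for the whole trial: "The Safety Analysis Set is the group of subjects who receive at least 1 dose of study drug", with at least one safety assessment after dosing. It is not divided by cohort. Section 9.7.1.4 lists clinical population as a baseline variable to be described within each treatment group of that set, so there the groups contain both cohorts.

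Section 9.7.1.8 then uses treatment group as the tabulation unit throughout. For adverse events, "The TEAEs will be summarized by treatment group on the Safety Analysis Set". For deaths, "TEAEs leading to death will be summarized by MedDRA SOC and preferred term for each treatment group". For serious events, "The number (percentage) of subjects with treatment-emergent SAEs will be summarized by MedDRA SOC and preferred term for each treatment group". Discontinuations due to adverse events, laboratory values, vital signs and ECGs follow the same pattern, and lymphocyte subsets are handled like other laboratory parameters and plotted by dose.

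One sentence in Section 9.7.1.8.2 does separate the cohorts. "Adverse events will be summarized by the following subgroups" is followed by three factors, the last being "and clinical population (MCI/Prodromal or mild to moderate AD".

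On allocation, Section 9.1 says "In Stage B, both cohorts will include separate placebo groups". Section 9.7.4 gives AD subjects 1:1:1:1 over placebo, 5, 15 and 50 mg in Stage A, but 1:1:1 over placebo, 15 and 50 mg in Stage B. MCI/Prodromal subjects have all four arms in equal ratio for the first 100. "Thereafter, randomization probabilities to each treatment group will be updated at each interim analysis", upward for placebo and the likely ED90 doses and downward for the other active arms.

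**The concern.** Randomization protects comparisons within a cohort. Once two cohorts with different arms and ratios are added together, it no longer balances disease stage across the pooled arms. If an outcome is more frequent, or a laboratory level different, in mild to moderate AD than in MCI, the arm with fewer AD subjects looks different even when the drug does nothing. The 5 mg arm is affected by design.

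Safety in both cohorts, including immunological and hematological parameters, is primary objective 2 (Section 8.1). Section 9.7.3, as revised by Amendment 03, has the sponsor unblinding safety data on an ongoing basis to decide on the rest of the study and the programme. Descriptive tables will therefore be read across doses. The protocol recognizes the hazard: Section 9.2.3 gives the risk of AD data confounding the MCI results as a reason for analysing the cohorts separately, and Section 9.7.1.6.2 keeps the AD efficacy comparison within AD subjects. The safety section has no equivalent rule beyond the adverse-event subgroup sentence.

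**Working it through.** **Inputs from the protocol**
- Stage A: 60 subjects, 1:1:1:1 within each cohort, target 15 per arm, no limit on either cohort (Synopsis, Number of Subjects; Section 9.1).
- Maximum of about 500 MCI/Prodromal and 200 AD subjects, Stage A included (Section 9.3).
- Stage B AD 1:1:1 without 5 mg; MCI 1:1:1:1 for the first 100, then adaptive (Section 9.7.4).

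**Assumed, because the protocol gives no figures**
- Event rates by cohort.
- An adaptive split after the first 100 of 40% placebo, 40% favoured dose and 10% for each other dose.

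**Step 1, the stated figure.** 60 / 4 = 15 per arm, which agrees with the protocol. AD subjects can receive 5 mg only in Stage A, so at most about 15 do.

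**Step 2, AD subjects per arm.** Let a be the number of AD subjects in Stage A, from 0 to 60.
- 5 mg: a/4, that is 0 to 15.
- Placebo, 15 mg and 50 mg: a/4 + (200 - a)/3. For a = 0 this is 66.7. For a = 60 it is 15 + 46.7 = 61.7.

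**Step 3, AD share of each arm** = AD / (AD + MCI). With 500 MCI in equal arms of 125:
- Placebo, 15 mg, 50 mg: 66.7/191.7 = 34.8% (a = 0); 61.7/186.7 = 33.0% (a = 60).
- 5 mg: 0% (a = 0); 15/140 = 10.7% (a = 60).

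Under the assumed adaptive split, placebo and the favoured dose each have 25 + 160 = 185 MCI subjects and the other doses 25 + 40 = 65.

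| Scenario | Placebo | 5 mg | 15 mg | 50 mg |
|---|---|---|---|---|
| 500 MCI, equal | 33.0-34.8% | 0-10.7% | 33.0-34.8% | 33.0-34.8% |
| 500 MCI, assumed adaptive split favouring 50 mg | 25.0-26.5% | 0-18.8% | 48.7-50.6% | 25.0-26.5% |
| 200 MCI, equal (enrolment stopped at the earliest success look) | 55.2-57.1% | 0-23.1% | 55.2-57.1% | 55.2-57.1% |

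**Step 4, crude gap with no drug effect** = (difference in AD share) x (AD rate - MCI rate). For 5 mg minus placebo, 500 MCI in equal arms:
- 10% in MCI, 20% in AD: (0 - 34.8%) x 0.10 = -3.5 points (a = 0); (10.7% - 33.0%) x 0.10 = -2.2 points (a = 60).
- 20% in MCI, 35% in AD: (0 - 34.8%) x 0.15 = -5.2 points (a = 0); (10.7% - 33.0%) x 0.15 = -3.3 points (a = 60).

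**Step 5, 15 mg minus placebo at 10% and 20%.** With equal MCI arms the shares are identical and the gap is 0. Under the assumed split favouring 50 mg it is (50.6% - 26.5%) x 0.10 = 2.4 points (a = 0) or (48.7% - 25.0%) x 0.10 = 2.4 points (a = 60). In that same scenario the gap for 5 mg minus placebo is (18.8% - 25.0%) x 0.10 = -0.6 points at a = 60, so adaptation can also shrink the 5 mg distortion.

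**Step 6, after stratification.** Within a cohort the AD share is the same in every arm, so each of these null gaps is 0 in expectation.

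**The case against.** The best answer is that the protocol already splits adverse events by clinical population in the section that contains the pooled rule. Deaths, SAEs and discontinuations due to adverse events are adverse events, so the sentence can be read to reach them. That stands as a fair reading, but not as a stated rule: the later sentences on those events name treatment group only. The sentence cannot reach laboratory values, ECGs or vital signs.

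It is also true that the summaries are descriptive, that Section 9.7.1.8 plans no between-arm test or risk difference, and that table layout is often settled in the SAP, which is not shown. This limits the point to wording and presentation. It does not remove it, because the tabulation rule itself is written here.

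Three stronger readings are tempting and not supported:
- A reader might infer that every comparison with placebo is distorted. With equal MCI arms, 15 and 50 mg against placebo are not.
- A reader might infer that a false safety signal is to be expected. No document shows that the unsplit outcomes depend on stage. For lymphocyte subsets, Appendix 5 attributes low baseline counts to age rather than disease, although it does not address change on treatment.
- A reader might infer that Phase 3 dose selection rests on these tables. Section 7 says only that the study's results will guide it, and Section 9.2.3 says each cohort is analysed independently for decisions.

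**Conclusion.** The point holds in limited form. Read literally, Section 9.7.1.8 gives pooled dose columns whose AD share differs: 33.0-34.8% on placebo, 15 mg and 50 mg against 0-10.7% on 5 mg, at the maximum cohort sizes with equal MCI allocation. Crude contrasts with 5 mg, and with 15 or 50 mg when adaptive allocation makes the MCI arms unequal, are confounded with disease stage for any outcome that varies by stage.

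The imbalance under equal MCI allocation follows from the design, given full enrolment. The resulting bias cannot be sized from the protocol. The gaps of -2.2 to -3.5 points and -3.3 to -5.2 points rest on assumed rates, and the 15 mg figure also on an assumed adaptive split. For adverse events the remedy is already partly in the text. The gap is clear for laboratory values, lymphocyte subsets, ECGs and vital signs, and a matter of unclear wording for deaths, SAEs and discontinuations. This is a cheap improvement, not a flaw that undermines the trial.

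**What to change.** In Section 9.7.1.8:
- State that the existing split by clinical population applies to every safety summary: deaths, SAEs, discontinuations due to adverse events, laboratory values, lymphocyte subsets, ECGs and vital signs. Show each cohort against its own placebo group.
- Where a between-arm figure combines the cohorts, give a cohort-stratified difference, for example Mantel-Haenszel or with common weights, instead of the difference in crude pooled percentages.
- Limit 5 mg comparisons in AD to subjects randomized in Stage A, the only AD subjects who could be assigned to that arm.

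No new data, subjects or visits are needed. The cost is more tables and fewer subjects in each, so rates for uncommon events will be less precise, especially in AD.
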